## 12. ADVERSE EVENTS AND DEVICE DEFICIENCIES

### 12.1 **DEFINITIONS**

The categories of adverse events are shown in **table 12.1-1**. The definitions for each of these categories are given in the subsequent sections.

This document contains information that is confidential and proprietary to Smith + Nephew PLC and Smith + Nephew, Inc. and is intended for use only by Smith + Nephew and its manufacturer. It shall not be reproduced or copied in whole or in part, nor shall the contents be disclosed by any means without prior written permission from Smith + Nephew, nor shall anyone make any use of it that is contrary to the expressed or implied wishes of Smith + Nephew.

Study Protocol	% smith&nephew
A prospective, multi-center, single arm PMCF study to evaluate the safety and performance of ENTACT ™ (Next Generation)	Number: ENTACT.ENT.PRO.SEP.2019.05
resorbable septal staple system for septoplasty	Version: 2.0, 27Aug2020
	Page: Page 59 of 94

## Table 12.1-1: Categories of Adverse Event

	NOT DEVICE- RELATED	DEVICE- OR PROCE	EDURE-RELATED
NON- SERIOUS	Adverse Event (AE)	Adverse Dev (ADI	ICE EFFECT E)
		Serious Adverse (SADE) (se	DEVICE EFFECT E 12.1.3)
SERIOUS	SERIOUS ADVERSE EVENT	ANTICIPATED	UNANTICIPATED
	(SAE)	ANTICIPATED SERIOUS ADVERSE DEVICE EFFECT (ASADE)	UNANTICIPATED SERIOUS ADVERSE DEVICE EFFECT (USADE)

### 12.1.1 Adverse Event

An Adverse Event (AE) is any untoward medical occurrence, unintended disease of untoward clinical sign (including abnormal laboratory findings) in subjects, users or other persons, whether or not causally related to the IP/Ancillary Product.

Note 1: This definition includes events related to the IP, comparator or ancillary products.

Note 2: This definition includes events related to the procedures involved.

Note 3: For users or other persons, this definition is restricted to events related to the IP

AE is used both to refer to AE which do not meet the definitions of Adverse Device Effects or Serious Adverse Events and as an umbrella term referring to adverse events of all classifications.

An AE can be any unfavorable and unintended sign (for example, an abnormal laboratory finding), symptom, or disease. For reporting purposes, emphasis is placed first and foremost on whether or not the event constitutes an untoward medical occurrence.

This document contains information that is confidential and proprietary to Smith + Nephew PLC and Smith + Nephew, Inc. and is intended for use only by Smith + Nephew and its manufacturer. It shall not be reproduced or copied in whole or in part, nor shall the contents be disclosed by any means without prior written permission from Smith + Nephew, nor shall anyone make any use of it that is contrary to the expressed or implied wishes of Smith + Nephew.

Study Protocol	>∕smith&nephew
A prospective, multi-center, single arm PMCF study to evaluate the safety and performance of ENTACT ™ (Next Generation)	Number: ENTACT.ENT.PRO.SEP.2019.05
resorbable septal staple system for septoplasty	Version: 2.0, 27Aug2020
	Page: Page 60 of 94

## 12.1.2 Adverse Device Effect

An Adverse Device Effect (ADE) is an adverse event that, in the opinion of the investigator, is related to the use of the IP.

Note 1: This definition includes adverse events resulting from insufficient or inadequate instructions for use, deployment, implantation, installation or operation, or any malfunction of the investigational medical device.

Note 2: This definition includes any event resulting from use error or from intentional misuse of the investigational medical device.

- **Not Related** An AE is considered to be not related to the use of an IP or the procedure when the effect is DEFINITELY UNRELATED or UNLIKELY to have any relationship to the use of the IP or the procedure;
- **Related** An AE is considered to be related to the use of an IP or the procedure when there is a POSSIBLE, PROBABLE, or DEFINITE relationship between the AE and the use of the IP or the procedure.

An ADE is further categorized depending on whether the criteria in **section 12.1.3 and 12.1.4** are met.

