#### 8.4.3 Investigator Training

Prior to the clinical trial, the clinical research associate (CRA), coordinating with the persons in charge of the study sites, will train the Investigators on the study protocol, making sure they are familiar with the use of investigational medical device, and implement subject enrollment strictly in accordance with the inclusion criteria and exclusion criteria, conduct relevant examinations according to the protocol requirements, also master all new device-related information found during the clinical trial, thus to minimize the interferential factors. The follow-up exams will be delegated to Investigators not involved in the procedure to reduce potential bias by the surgeon.

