## 12.1.3 Serious Adverse Events and Serious Adverse Device Effects

An AE or ADE is considered a **Serious** Adverse Event (SAE) or **Serious** Adverse Device Effects (SADE) if, in the view of either the Investigator or the Sponsor, it:

- a) led to death,
- b) led to serious deterioration in the health of the subject, that either resulted in
  - 1) a life-threatening illness or injury, or

This document contains information that is confidential and proprietary to Smith + Nephew PLC and Smith + Nephew, Inc. and is intended for use only by Smith + Nephew and its manufacturer. It shall not be reproduced or copied in whole or in part, nor shall the contents be disclosed by any means without prior written permission from Smith + Nephew, nor shall anyone make any use of it that is contrary to the expressed or implied wishes of Smith + Nephew.

Study Protocol	> ∕ smith&nephew
A prospective, multi-center, single arm PMCF study to evaluate	Number:
the safety and performance of ENTACT™ (Next Generation)	ENTACT.ENT.PRO.SEP.2019.05
resorbable septal staple system for septoplasty	Version: 2.0, 27Aug2020
	Page: Page 61 of 94

- o 2) a permanent impairment of a body structure or a body function, or
- o 3) in-patient or prolonged hospitalization, or
- 4) medical or surgical intervention to prevent life-threatening illness or injury or permanent impairment to a body structure or a body function,
- c) led to foetal distress, foetal death or a congenital abnormality or birth defect

Note: Planned hospitalization for a pre-existing condition, or a procedure required by the study protocol, without serious deterioration in health, is not considered a serious adverse event.

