## 12.1.5 Severity

The severity of every AE will be assessed by the PI or medically qualified site staff to whom the responsibility has been delegated and documented on the delegation of authority log. AE should be classified as mild, moderate, or severe, regardless of whether or not the AE are considered to be serious or non-serious. The classification should be based on the following definitions:

- Mild An event is mild if the subject is aware of, but can easily tolerate the sign or symptom;
- Moderate An event is moderate if the sign or symptom results in discomfort significant enough to cause interference with the subject's usual activities; CONFIDENTIAL AND PROPRIETARY

This document contains information that is confidential and proprietary to Smith + Nephew PLC and Smith + Nephew, Inc. and is intended for use only by Smith + Nephew and its manufacturer. It shall not be reproduced or copied in whole or in part, nor shall the contents be disclosed by any means without prior written permission from Smith + Nephew, nor shall anyone make any use of it that is contrary to the expressed or implied wishes of Smith + Nephew.

Study Protocol	% smith&nephew
A prospective, multi-center, single arm PMCF study to evaluate the safety and performance of ENTACT ™ (Next Generation) resorbable septal staple system for septoplasty	Number: ENTACT.ENT.PRO.SEP.2019.05
	Version: 2.0, 27Aug2020
	Page: Page 62 of 94

**Severe** - An event is severe if the sign or symptom is incapacitating and results in the subject's inability to work or engage in their usual activities.

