## 12.3 **Reporting Procedures**

AE of any kind and DD will be recorded in the applicable CRF and source notes. The Investigator will evaluate all AE for relationship to the device and procedure, if applicable, seriousness, and severity. The following timescales should be followed for the AE/DD information to be submitted/entered into the CRF and reported to the Sponsor or designee (see figure 12.3-1 and Figure 12.3-2):

- ADE and DD without unreasonable delay
- SAE, SADE and DD with potential to cause SADE immediately (i.e. within 24 hours of the investigator being informed about the event)

For ADE and DD, details of the product/procedure related to the event will be included and where applicable, pictures taken of the device. The deficient product should be retained for return to S+N unless it is contaminated (e.g., used dressings must not be retained). Updates to submitted information will be recorded in the CRF according to the timescales above.

This document contains information that is confidential and proprietary to Smith + Nephew PLC and Smith + Nephew, Inc. and is intended for use only by Smith + Nephew and its manufacturer. It shall not be reproduced or copied in whole or in part, nor shall the contents be disclosed by any means without prior written permission from Smith + Nephew, nor shall anyone make any use of it that is contrary to the expressed or implied wishes of Smith + Nephew.

Study Protocol	% smith&nephew
A prospective, multi-center, single arm PMCF study to evaluate the safety and performance of ENTACT ™ (Next Generation) resorbable septal staple system for septoplasty	Number: ENTACT.ENT.PRO.SEP.2019.05
	Version: 2.0, 27Aug2020
	Page: Page 63 of 94

All adverse events will be reviewed by a medically qualified person appointed by the Sponsor to determine which, if any, meet criteria for expedited reporting to the regulatory authorities.

The investigator will inform the IRB/ Independent Ethics Committee (IEC) of adverse events according to the IRB/IEC requirements.

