#### CONFIDENTIAL AND PROPRIETARY

This document contains information that is confidential and proprietary to Smith + Nephew PLC and Smith + Nephew, Inc. and is intended for use only by Smith + Nephew and its manufacturer. It shall not be reproduced or copied in whole or in part, nor shall the contents be disclosed by any means without prior written permission from Smith + Nephew, nor shall anyone make any use of it that is contrary to the expressed or implied wishes of Smith + Nephew.

Study Protocol	Smith&nephew
A prospective, multi-center, single arm PMCF study to evaluate the safety and performance of ENTACT ™ (Next Generation)	Number: ENTACT.ENT.PRO.SEP.2019.05
resorbable septal staple system for septoplasty	Version: 2.0, 27Aug2020
	Page: Page 64 of 94

Unanticpated Serious Adverse unanticipated **Device Effect** (USADE) nvestigator` Complete CRF sesses whether and alert S&N SADE is Related IMMEDIATELY anticipated Anticipated Serious Adverse Investigator **Device Effect** assesses device relationship (ASADE) Record Serious details in Λ subject s Not Related medical Serious Adverse Site Investigator records Event (SAE) aware assesses of AE seriousness Complete CRF and alert S&N dverse Device Non-serious without Effect (ADE) unreasonable Related delay. Investigator assesses device relationship Record Not Related information in Adverse Event patient CRF (AE) according to usual timescales.

Figure 12.3-1: Evaluation and Reporting of AE

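### Device-relatedness is decided by the investigator alone, who may be the operating surgeon; neither the sponsor's medical review nor the non-operating-examiner rule reaches that decision

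*Combined protocol and SAP*

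**What the plan says.** Relatedness is assigned to one party in three places. By section 12.1.2, an ADE "is an adverse event that, in the opinion of the investigator, is related to the use of the IP". Section 12.3 states: "The Investigator will evaluate all AE for relationship to the device and procedure, if applicable, seriousness, and severity". The corresponding step in Figure 12.3-1 reads "Investigator assesses device relationship".

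Seriousness follows a different rule. Section 12.1.3 treats an event as serious "if, in the view of either the Investigator or the Sponsor, it" meets a listed criterion, so one party's view is enough. For severity, section 12.1.5 says: "The severity of every AE will be assessed by the PI or medically qualified site staff".

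Two safeguards sit nearby. Section 12.3 has every adverse event "reviewed by a medically qualified person appointed by the Sponsor to determine which, if any, meet criteria for expedited reporting to the regulatory authorities". Section 8.4.3 says: "The follow-up exams will be delegated to Investigators not involved in the procedure to reduce potential bias by the surgeon". Rationale 4 of the amendment (section 21.1.2) records that this sentence answered the notified body's concern about surgeon bias.

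Section 8.3.3 names device-related re-intervention and device-related events as safety endpoints. Section 10.5 tabulates device-related and serious device-related events alongside all-cause counts.

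**The concern.** The study has one arm and no blinding (8.2), so there is no control rate against which to judge device harm. The relatedness call is what separates device events from ordinary surgical events in the ADE and device-related re-intervention tables. The person making it may have performed the operation and would then be judging between the stapler and their own work. The protocol accepts that this position can bias a nasal examination and acts on it, but it does not carry the remedy over to causality or severity.

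The call also controls what happens next. An unanticipated serious ADE must first be an ADE (12.1.4). The sponsor can make an event serious under 12.1.3, but no provision lets it make an event device-related. Non-serious device-related events go to the sponsor without unreasonable delay, while non-serious unrelated ones follow usual timescales (12.3, Figure 12.3-1). Study data collection ends at re-intervention (notes to Table 9.1.1-1), so no later study data would test the attribution of a re-intervention.

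**Working it through.** The plan gives no misattribution rate, so the check is mainly a comparison of text, with a short calculation for scale.

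**Who decides what**

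| Judgement | Assessor | Second view | Operating surgeon excluded? |
|---|---|---|---|
| Device-relatedness (12.1.2, 12.3, Figure 12.3-1) | Investigator | None stated | No |
| Severity (12.1.5, 12.3) | PI or delegated site staff | None stated | No |
| Seriousness (12.1.3) | Investigator or sponsor | Yes, either suffices | No |
| Nasal examination at follow-up (8.4.3) | Investigator not in the procedure | Not applicable | Yes |
| Expedited reporting (12.3) | Sponsor's medical reviewer | Not applicable | Not applicable |

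The first two rows are the gap. Section 8.4.3 covers follow-up exams only, so it cannot reach events on the day of surgery, when safety assessment is also scheduled (Table 9.1.1-1, section 9.1.2).

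**What counts as device-related**

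The documents are mixed.
- The ADE definition in 12.1.2 refers to the investigational product only.
- The Related category in the same section covers the product or the procedure and starts at a possible relationship.
- Table 12.1-1 puts device-related and procedure-related events in one ADE column.
- Section 8.3.3 lists device-related endpoints, and section 10.5 summarizes relationship to the device.

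Under Table 12.1-1, an event relabelled from device to procedure stays an ADE. Under the 12.1.2 definition it leaves the ADE count.

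**Scale**

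Inputs: 40 subjects enrolled (section 11). Enrolled means consented and treated (7.6), and the safety population is everyone who received the device (10.2), so the denominator is 40.

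One subject reclassified: 1/40 = 2.5 percentage points.

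Exact (Clopper-Pearson) 95% limits for x of n: lower = 2.5% quantile of Beta(x, n−x+1); upper = 97.5% quantile of Beta(x+1, n−x). As a check on the method, this reproduces the intervals printed in Table 4.4.1-1: 2/40 gives 0.61% to 16.92%, and 4/40 gives 2.79% to 23.66%.

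| Subjects counted as device-related | Rate | Exact 95% CI |
|---|---|---|
| 4/40 | 10.0% | 2.8% to 23.7% |
| 3/40 | 7.5% | 1.6% to 20.4% |
| 2/40 | 5.0% | 0.6% to 16.9% |
| 1/40 | 2.5% | 0.1% to 13.2% |

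As an assumption only: if 4 subjects truly had device-related events and 25%, 50% or 75% were called unrelated to the device, the count would be 3, 2 or 1. The table can equally be read upward for events wrongly blamed on the stapler.

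**The case against.** The strongest case against is that the plan already has several protections.
- A medically qualified person sees every adverse event, and the sponsor may ask for medical records and operative notes (12.3).
- A possible relationship counts as related, which works against under-attribution.
- Notes 1 and 2 of 12.1.2 count deployment problems and use error as device effects, which leaves less room to call a stapling event procedural.
- Adverse-event recording is part of the same follow-up visits as the nasal examination (9.1.3 to 9.1.5), so the non-operating examiner may well handle events found there.
- Different rules for seriousness and causality are not a contradiction, and a sponsor-appointed reviewer is not independent.

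Most of this stands, and it narrows the point. A reader might infer that attribution goes wholly unchecked; these protections show that is too strong. A reader might also infer that device-related results will be biased low. Nothing in the documents settles the direction: a surgeon choosing between the device and their own technique could err either way.

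What does not fall away is that none of these provisions lets anyone revise a relatedness call or keeps the operating surgeon from making it. That the follow-up examiner might assign causality is a reasonable reading of a silence in 8.4.3, but it is not a rule.

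**Conclusion.** The point holds as a limited design weakness. Relatedness is a single-assessor judgement that the operating surgeon may make. The sponsor's review is confined to expedited reporting, and the examiner separation in 8.4.3 is not extended to causality or severity. ADEs and device-related re-intervention are exposed, at 2.5 points per reclassified subject out of 40. The scenarios starting from 4 subjects rest on assumed shifts and are not estimates.

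All-cause adverse-event and serious adverse-event counts do not move with a relatedness call. Because 4/40 and 2/40 are also entries in Table 4.4.1-1, a reader might infer that misattribution could hide a breached tolerance limit. Section 4.4.1 does not support this: it compares adverse-event occurrences with the limits and states no device-related filter.

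The primary endpoint has its own device-or-procedure attribution in 10.4.1. It does not use the ADE definition, and this point does not rest on it.

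**What to change.** 1. In 12.1.2, apply the either-party principle of 12.1.3: an event is device-related if the investigator or the sponsor's existing medical reviewer (12.3) considers it at least possibly related to the device. The reviewer may upgrade the investigator's call but not downgrade it, which also limits the concern that this reviewer is not independent. Record both opinions and list disagreements.
2. In 12.1.5 and 12.3, have relatedness and severity of events found at follow-up graded by the non-operating investigator who does that exam under 8.4.3.
3. Reconcile Table 12.1-1 and the Related definition, which join device and procedure, with the product-only ADE definition, so that device and procedure relatedness are recorded separately.

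The cost is protocol wording and one extra field on a review that already covers every adverse event. It uses assessors the protocol already provides for. The downside is that the device-related count may be slightly higher.

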This document contains information that is confidential and proprietary to Smith + Nephew PLC and Smith + Nephew, Inc. and is intended for use only by Smith + Nephew and its manufacturer. It shall not be reproduced or copied in whole or in part, nor shall the contents be disclosed by any means without prior written permission from Smith + Nephew, nor shall anyone make any use of it that is contrary to the expressed or implied wishes of Smith + Nephew.

Study Protocol	> ∕ smith&nephew
A prospective, multi-center, single arm PMCF study to evaluate the safety and performance of ENTACT™ (Next Generation) resorbable septal staple system for septoplasty	Number: ENTACT.ENT.PRO.SEP.2019.05
	Version: 2.0, 27Aug2020
	Page: Page 25 of 94

ENTACT Septal Stapler group (9.9%) and the subgroups such as silicone splint group (9.7%), suture group (12.7%), and the tamponade group (9.5%) in the non-stapler group.

Since the ENTACT (Next Generation) Septal Stapler utilizes the same staples and a similar delivery mechanism to the previous ENTACT Septal Stapler, it is anticipated that the Next Generation device will perform the same as the previous generation device.

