## 8.3.3 Safety Endpoints

Following are the safety endpoints for this study:

- Device-related re-intervention;
- All adverse events (AEs) occurring from the time of surgery until re-intervention or study completion;
- Device related AEs (ADEs) and serious adverse events (SAE's);
- Device deficiencies (DDs)

All AEs will be categorized in terms of seriousness and relatedness to the study device or to the surgical procedure. All Serious Adverse Device Effects will be further categorized as Anticipated or Unanticipated. The definitions for each of these categories are based on ISO 14155:2011.

This document contains information that is confidential and proprietary to Smith + Nephew PLC and Smith + Nephew, Inc. and is intended for use only by Smith + Nephew and its manufacturer. It shall not be reproduced or copied in whole or in part, nor shall the contents be disclosed by any means without prior written permission from Smith + Nephew, nor shall anyone make any use of it that is contrary to the expressed or implied wishes of Smith + Nephew.

Study Protocol	> ∕ smith&nephew
A prospective, multi-center, single arm PMCF study to evaluate the safety and performance of ENTACT™ (Next Generation) resorbable septal staple system for septoplasty	Number: ENTACT.ENT.PRO.SEP.2019.05
	Version: 2.0, 27Aug2020
	Page: Page 45 of 94

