# 9.1.3 Follow-up Visit (Visit 3) Day 5 (± 2 days)

- Query subject regarding any changes in general health and the use of concomitant medications.
- 2. Record assessment of nasal cavity.

This document contains information that is confidential and proprietary to Smith + Nephew PLC and Smith + Nephew, Inc. and is intended for use only by Smith + Nephew and its manufacturer. It shall not be reproduced or copied in whole or in part, nor shall the contents be disclosed by any means without prior written permission from Smith + Nephew, nor shall anyone make any use of it that is contrary to the expressed or implied wishes of Smith + Nephew.

Study Protocol	> √ smith&nephew
A prospective, multi-center, single arm PMCF study to evaluate the safety and performance of ENTACT™ (Next Generation) resorbable septal staple system for septoplasty	Number: ENTACT.ENT.PRO.SEP.2019.05
	Version: 2.0, 27Aug2020
	Page: Page 50 of 94

- If any adverse device effects or device deficiencies are observed or reported, they must be recorded as instructed in Section 12, adverse events and device deficiencies. Also record concomitant medications/therapies used to treat AEs.
- 4. Complete NOSE score assessment and VAS pain score.
- 5. Instruct the subject on follow-up procedures, including returning the treatment facility at 21 days post-operative (± 7) days for follow-up visit.
- 6. If applicable, complete an End of Study CRF.

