### Adverse Events

The number of subjects reporting: adverse events, serious adverse events, severe adverse events, device-related adverse events, serious device-related adverse events, unanticipated adverse events, and serious unanticipated adverse events will be summarized. In addition, for each adverse event, the following will be summarized: severity, the relationship to the investigational device, outcome and duration of the resolved adverse events and the duration of the adverse events at trial discontinuation.

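### The protocol contradicts itself on whether a procedure-only event is an Adverse Device Effect, so the device-related AE endpoint is undetermined and could absorb ordinary surgical complications

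*Combined protocol and SAP*

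**What the plan says.** Several places in the protocol bear on what counts as an ADE.

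- Section 12.1.2, opening sentence: an ADE "is an adverse event that, in the opinion of the investigator, is related to the use of the IP". This is device-only.
- Section 12.1.2, relatedness rule: an AE counts as "related to the use of an IP or the procedure when there is a POSSIBLE, PROBABLE, or DEFINITE relationship" with either one. This is a single test covering two causes.
- Table 12.1-1: one column, headed as not device-related, holds AE and SAE. The other has a heading that begins "DEVICE- OR PROCE" (the last word is broken in the extracted text) and holds ADE, SADE, ASADE and USADE.
- Section 8.3.3: the safety endpoints include "Device related AEs (ADEs) and serious adverse events", so device-related AEs and ADEs are treated as the same thing. The section also says that all AEs will be categorised by relatedness to the device or to the surgery.
- Figure 12.3-1: the branch into ADE or SADE depends on the investigator's view of the device relationship alone.
- Section 12.3: the investigator evaluates each AE for relationship to the device and, where applicable, the procedure.
- Section 10.5: the tables will count subjects with "device-related adverse events, serious device-related adverse events" and summarise each event's relationship to the device. No procedure-related category is listed.

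**The concern.** Device-related AEs are a named safety endpoint with a planned tabulation. The study has one arm, so no comparator can separate complications of septoplasty from those of the stapler afterwards. The investigator's attribution is the only means of doing so. If the protocol does not say whether a complication attributed only to the surgery is an ADE, two sites can both follow it and code the same event differently, and Section 10.5 as planned would not show the mixing.

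The label also has consequences outside the tables. In Section 12.3 and Figure 12.3-1, a non-serious ADE must reach the sponsor promptly, while a non-serious unrelated AE follows the routine timetable. A serious procedure-only event is an SAE on one reading. On the other it is a SADE that must also be classed as anticipated or unanticipated.

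The sponsor evidently values the distinction. For the primary endpoint, Section 10.4.1 collects whether septum appearance and re-intervention are due to the device or the procedure.

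**Working it through.** No stated sample size, power or error rate depends on this point, so there is no figure of the plan to reproduce. The check sets the texts side by side for one test case: an event the investigator attributes to the surgery and not to the stapler.

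| Place | Basis | Non-serious | Serious |
|---|---|---|---|
| 12.1.2, opening sentence | device | AE | SAE |
| 8.3.3, endpoint | device | not in the ADE endpoint | not in the ADE endpoint |
| Figure 12.3-1 | device | AE | SAE |
| Table 12.1-1, not-device-related column | device | AE | SAE |
| 12.1.2, relatedness rule | device or procedure | related | related |
| Table 12.1-1, other column | device or procedure | ADE | SADE, then ASADE or USADE |

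The two table columns are not complementary: a procedure-only event satisfies both headings. No sentence gives one text precedence.

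**Illustration of size.** Inputs: N = 40 (Section 11), and complication rates without the stapler in the cited retrospective comparison, 9.5% (tamponade), 9.7% (silicone splint) and 12.7% (suture) (Section 4.2.2). Assumption: these rates approximate the background of surgical complications in this study.

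Expected subjects with a complication = N × p; probability of at least one = 1 − (1 − p)^40; the range is the central 95% of the binomial distribution.

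| p | 40 × p | P(at least one) | 95% range |
|---|---|---|---|
| 0.095 | 3.8 | 98.2% | 1 to 8 |
| 0.097 | 3.88 | 98.3% | 1 to 8 |
| 0.127 | 5.08 | 99.6% | 1 to 10 |

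So the ambiguous case is very likely to arise, in about 4 to 5 subjects.

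**How many change label.** Let q be the share of these subjects whose complication is rated at least possibly device-related. Those stay ADEs on either reading. If all are counted under the table's wider heading, the number that differs between readings is 40 × p × (1 − q). The documents give no value for q, so the range is:

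- q = 0: 3.8 to 5.1 subjects
- q = 0.5: 3.8 × 0.5 = 1.9 to 5.08 × 0.5 = 2.5 subjects
- q = 1: none

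**The case against.** The strongest reply is that the operative text is mostly device-only: the ADE sentence, the endpoint, the flowchart and the relationship summarised in Section 10.5. Sections 8.3.3 and 12.3 already call for relatedness to device and procedure, and the rule in 12.1.2 could be read as one rating scale applied to each in turn. If the CRF holds two fields, the counts can be separated. The CRF is not in the documents, so this cannot be settled. The reply shows that the damage may be avoidable; it does not remove the contradiction. A later SAP could add a table but could not restore a distinction that sites did not record.

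Four stronger readings are tempting and are not supported.

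- A reader might infer that the endpoint will absorb surgical complications. That follows from the table but not from the ADE sentence or Figure 12.3-1, so it only could.
- A reader might contrast 4/40 (10%, exact 95% CI 2.8% to 23.7%) with 0/40 (0% to 8.8%). That is an extreme. Events rated possibly device-related stay ADEs under any repair, and Section 4.4 lists hematoma, infection and tissue reaction among the device's potential adverse effects.
- A reader might take the visit steps ("If any adverse device effects or device deficiencies are observed or reported, they must be recorded as instructed in Section 12") to mean that other AEs go unrecorded. The steps do not say only. The schedule of events in Section 9.1 requires AE, SAE, ADE and DD assessment from surgery onward, and Section 12.3 and Appendix 21.5 require every AE to be recorded.
- A reader might call this the main safety figure for the CE-mark file. No passage says so. The numerical benchmarks in Table 4.4.1-1 are by event type with no relatedness filter stated, and total AE and SAE counts do not depend on the ADE label.

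**Conclusion.** The point stands as an internal contradiction with a practical consequence. The documents support both a device-only and a device-or-procedure meaning of ADE, and a named safety endpoint takes a different value under each. On the cited rates without the stapler, about 4 to 5 of 40 subjects would have a complication with no device effect. Between none and all of these could change label, depending on the device ratings.

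That size is an illustration. It assumes that rates from a retrospective comparison carry over to this population, and that complications under other closure methods represent surgical background, although those methods may cause some of their own.

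The direction is to overstate device-related AEs, which is conservative for the device but blurs attribution. Sample size is unaffected. The primary analysis is also unaffected, because Section 10.4.1 has its own device-or-procedure rule. The point should be corrected, but it does not threaten the study's main result.

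**What to change.** - Section 12.1.2: rate relationship to the device and relationship to the procedure as two separate items on the same scale. State that only the device rating, at possible or higher, defines ADE, SADE, ASADE and USADE.
- Table 12.1-1: retitle the two columns *not device-related* and *device-related*, so that they are complementary and match Figure 12.3-1. Procedure-only events then remain AE or SAE.
- Section 10.5: tabulate procedure-related AEs separately from device-related AEs.
- Minor consistency edit: align the visit steps in Sections 9.1.2 to 9.1.5 with the schedule of events and Section 12.3, so that they refer to all adverse events.

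In the protocol this is wording plus one added tabulation, because Sections 8.3.3 and 12.3 already ask for relatedness to device and procedure. The sponsor should check that the CRF has two relationship fields; if it has one, a field must be added.
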